Blood and urine specimens will be sent to LabCorp for processing. The results of laboratory blood and urine tests will not routinely be given to participants to send or be sent to their physician to include in their medical record. However, if the subject's lab results are outside the acceptable range for participation in the study the Physician/P.A. will send the subject a medical exclusion letter and a copy of the lab results. Participants who are accepted into the study but need medical follow up due to minor abnormalities in lab results will also be informed by letter from the Physician/P.A. A copy of the laboratory results will be included with the letter, which will also indicate that the condition does not interfere with his/her participation in the study.

The time commitment for subjects is 16 weeks: 4 weeks of pre-cessation treatment before the scheduled Quit Day and 12 weeks of additional post-Quit Day treatment, plus one follow-up session at six months (if eligible) after the Quit Day.

Questionnaires will be completed within REDCap on a desktop computer in the Center office. The technician will log on to the REDCap site and will open the questionnaires for the subjects. Subjects will only have access to their questionnaires. Access to any other websites will be blocked by Psychiatry Information Technology.

Session P1

The first study visit will take place approximately one week after the screening visit. Subjects will complete baseline questionnaires and will be randomized to either Group A (nicotine patch + lorcaserin) or Group B (nicotine patch + placebo). Subjects will be tested for exhaled air carbon monoxide and smoking related chemicals in the saliva. They will also have their blood pressure, heart rate and weight measured. Females of child bearing potential will also complete a urine pregnancy test which must be negative in order to continue study participation. Subjects will also complete questionnaires rating craving, withdrawal symptoms, side effects, and sensory experience.

Subjects will be given a supply of study medications (depending on randomization) to use for 2 weeks and will receive verbal and written instructions on how to take them.

Subjects will also be given diaries to record medication use and the number of cigarettes smoked each day and will be instructed to return the diaries at the next visit. They will also be asked to return any unused medications for proper disposal and compliance monitoring.

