Subjects will be called within three days after the first day of treatment to make sure that medications are being used as directed.

Session P2

The second study visit will take place 2 weeks after the first visit. Subjects will be tested for exhaled air carbon monoxide and smoking related chemicals in the saliva. Subjects

will also have their blood pressure, heart rate and weight measured. In addition, they will also complete questionnaires rating craving, withdrawal symptoms, side effects, and sensory experience.

A laboratory session will be conducted at this visit. Participants will be asked to refrain from smoking after midnight the night before the session. After an additional 2 hour period in which subjects refrain from smoking, withdrawal symptoms will be assessed as well the ability to delay smoking in a simulated smoking lapse paradigm validated by McKee et al (2012). In this paradigm smokers are allowed to smoke but are offered a monetary incentive to delay smoking, which decreases over time in the session.

Subjects in both Group A and Group B will be given a supply of study medications (nicotine patch + lorcaserin). Following the P2 laboratory session, the group that received nicotine patch + placebo will be switched to receiving nicotine patch+ lorcaserin, and the nicotine patch+ lorcaserin group will continue receiving nicotine patch+ lorcaserin, for an additional 2 weeks leading up to a scheduled target quit-smoking date (TQD).

Subjects will also be given diaries to record medication use and the number of cigarettes smoked each day and will be instructed to return the diaries at the next visit. They will also be asked to return any unused medications for proper disposal and compliance monitoring.

Session P3 (the day before Quit Day)

The third study visit will take place 2 weeks after the second visit (and one day prior to the Quit Day). Subjects will be tested for exhaled air carbon monoxide and smoking related chemicals in the saliva. Subjects will also have their blood pressure, heart rate and weight measured. Females of child bearing potential will also complete a urine pregnancy test which must be negative in order to continue study participation. They will also complete questionnaires rating craving, withdrawal symptoms, side effects, and sensory experience.

Subjects will be dispensed a sufficient supply of nicotine patches and lorcaserin to last until the next scheduled visit.

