Subjects will also be given diaries to record medication use and the number of cigarettes smoked each day and will be instructed to return the diaries at the next visit. They will also be asked to return any unused medications for proper disposal and compliance monitoring. In addition, they will be given forms to be completed on their Quit Day. They will be asked to return these forms at their next visit.

Sessions C1-C4

Session C1 will take place 1 week after Session P3. Session C2 will take place 2 weeks after C1. Session C3 will occur 3 weeks after C2, and Session C4 will occur 4 weeks after C3.

Subjects will be tested for exhaled air carbon monoxide and smoking related chemicals in the saliva. Subjects will also have their blood pressure, heart rate and weight measured. In addition, they will also complete questionnaires rating craving, withdrawal symptoms, side effects, and sensory experience.

At Sessions C2 and C3 females of child bearing potential will complete a urine pregnancy test which must be negative in order to continue study participation.

At Sessions C1-C3 subjects will be dispensed a sufficient supply of nicotine patches and lorcaserin to last until the next scheduled visit. At session C4 subjects will be given instructions for tapering off of the patch. They will be given a 1 week supply of 14mg nicotine patches and a 1 week supply of 7 mg nicotine patches. A technician will call them 2 weeks after the C4 session to follow up on the patch tapering process.

Subjects will also be given diaries to record medication use and the number of cigarettes smoked each day and will be instructed to return the diaries at the next visit. They will also be asked to return any unused medications for proper disposal and compliance monitoring.

Six-month Follow-up

Study participants will be contacted by phone, letter or email six months after their Quit Day and asked about their current smoking behavior, as well as their smoking behavior since their last session. Those subjects who report continuous or point abstinence (no smoking in the previous seven days) and have not used any smoking cessation aid will be asked to return to the laboratory for a brief follow-up session. This session will include an expired air CO reading; blood pressure, heart rate and weight measurements; collection of a saliva sample; and completion of several questionnaires.

SUBJECT IDENTIFICATION:

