Less likely

Lorcaserin HCl may also cause other, potentially serious side effects, including:

- Serotonin Syndrome or Neuroleptic Malignant Syndrome (NMS)-like reactions.
- Valvular heart disease
- Changes in your attention or memory
- Depression or thoughts of suicide
- Low blood sugar (hypoglycemia)
- (For Men) Painful erections (priapism)
- Slow heartbeat
- Decreases in your blood cell count
- Increase in prolactin
- Pulmonary hypertension (high blood pressure in the lungs)

Increases in the proportion of animals with tumors of some tissues, including breast, brain, thyroid gland, liver, skin and nerve sheath, were found in rats, but not mice, given lorcaserin HCl for 2 years at doses which produced blood levels higher than in humans. The relevance of tumors in rats to humans is unknown.

Subjects will be monitored throughout the duration of the study for side effects and severe adverse effects (SAEs). They will be instructed to report any side effects to the study technicians, who will communicate these reports immediately to the medical staff. The most appropriate course of action will be determined, which may include options for dose reduction or termination of treatment. Participants will be reminded that they have the option to withdraw from the study at any time. Subjects will also be given the 24 hour emergency contact numbers in the event that side effects or adverse events occur between sessions. SAEs will be reported to the IRB and will be monitored until resolution or stabilization.

Needle stick / Blood drawing: The risks associated with venipuncture are minimal, and include momentary discomfort and/or bruising. Infection, excess bleeding, clotting, and fainting are also possible, although unlikely.

SERIOUS ADVERSE EVENT REPORTING PLAN

The Principal Investigator will report all serious adverse events relating to the study in an expedited manner to the Duke University Health System (DUHS) Institutional Review Board (IRB) office, and all applicable regulatory authorities in accordance with the Center's standard operating procedures.

COSTS TO PARTICIPANTS

There are no costs to participants for taking part in this study. All the study costs, including any study medications and procedures related directly to the study, will be paid for by the research grant awarded to Duke University. The active lorcaserin and placebo lorcaserin tablets will be supplied by Eisai. The nicotine patch will be purchased from Duke Outpatient Pharmacy.

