- If BP > 160/100 for 2 consecutive sessions, then CSC will provide either weekly BP checks or request that the participant have his/her BP checked weekly by PCP, local pharmacy, or home machine and call us with results. The physician assistant will discuss these results with the study physician.
- A blood pressure memo to file form will be completed if BP>160/100 for 3 readings per center approved procedure.

Data Safety Monitoring Plan (DSMP)

We plan to exclude potential participants who take drugs that could interact with lorcaserin by increasing the risk of serotonin syndrome.

To address potential safety issues in addition to collection of the primary study outcomes, severe side effects and adverse events potentially associated with the study will be examined, recorded and then reported to the IRB in a manner consistent with Duke HRPP policies. The principal investigator will be responsible for monitoring data collection and safety of this study.

Data collection for this study will be carried out at the Durham clinical site of the Duke Center for Smoking Cessation (CSC). All members of the study team will complete research integrity (“code of conduct”) and CITI (Collaborative Institutional Training Initiative) Human Research Curriculum and clinical laboratory safety training as required by Duke University Medical Center. All study staff who are involved in data collection, management, and processing will be thoroughly trained following standards of procedures prior to working on this project.

Study staff responsible for data collection will use a checklist for completion for each study visit of each participant. Missing Data Forms, along with explanations should missing data occur, will be completed by the study staff for each study visit.

Microsoft Access will be used for logging subject information (Enrollment Log, Visit Log, etc.). Data will be entered by the study staff. The key study personnel will further examine the computerized data entries and original records for accuracy and completion.

Emergency Unblinding

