This is a blinded protocol such that all participants and all study personnel except for the Clinical Research Coordinator and the Research Program Leader are blinded to group allocation. During specific circumstances it will be necessary to unblind other study personnel, such as study team medical personnel. Emergency unblinding will occur under the discretion of the study physician (or one of the study physician assistants) in any situation in which unblinding is deemed necessary to ensure or promote the safety of a study participant. The decision to unblind for safety reasons may occur for a number of reasons and it is not possible to enumerate all potential circumstances. Examples of reasons for unblinding to ensure participant safety include situations in which it is necessary to know which study drugs the subject was taking in order to manage the side effect(s), advise the subject on the risk of future negative drug reactions, uncover potential safety information about the drug, and/or determine whether the adverse event

is study related. In those situations, the Clinical Research Coordinator or Research Program Leader will inform the study physician (or physician assistant handling the event) of that subject's treatment condition. If unblinding occurs, that subject's data will be censored and will not be included in final data analyses.

DATA STORAGE & CONFIDENTIALITY

Any PHI collected prior to documentation of informed consent will be de-identified if the potential subject does not qualify for this study. Please refer to the "Request for Waiver of Documentation of Informed Consent".

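### The adverse-event recording rule turns on severity or association with the study, relatedness may be judged after a code break, and the serious-event wording is inconsistent

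*Combined protocol and SAP*

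**What the plan says.** Four parts of the protocol bear on this.

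- **Data Safety Monitoring Plan.** The recording sentence is "severe side effects and adverse events potentially associated with the study will be examined, recorded", after which such events go to the IRB. No other sentence says which adverse events are recorded.
- **Risk/Benefit Assessment.** Participants are monitored for "side effects and severe adverse effects (SAEs", where the abbreviation is expanded as severe, not serious. The same paragraph ends by sending SAEs to the IRB and following them until resolved or stable, with no relatedness condition. It also says of participants: "They will be instructed to report any side effects to the study technicians, who will communicate these reports immediately to the medical staff".
- **Serious Adverse Event Reporting Plan.** "The Principal Investigator will report all serious adverse events relating to the study in an expedited manner". Here the term is serious, and the sentence is conditional on relation to the study.
- **Emergency Unblinding.** Unblinding is at the discretion of the study physician or a physician assistant. The listed examples include to "uncover potential safety information about the drug, and/or determine whether the adverse event" is study related. The data of any unblinded participant are then left out of the final analyses.

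Separately, side effects are rated by questionnaire at Session P1 ("Subjects will also complete questionnaires rating craving, withdrawal symptoms, side effects, and sensory experience"), and likewise at P2, P3 and C1-C4 ("In addition, they will also complete questionnaires rating craving, withdrawal symptoms, side effects, and sensory experience"). The Data Analysis section plans to tabulate side-effect frequencies, with no severity or relatedness condition.

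**The concern.** Tolerability of the combination is Aim 2, and the results are meant as pilot data for a larger trial. The Risk/Benefit Assessment cites no trial data on lorcaserin given with a nicotine patch. It infers safety from smokers who are assumed to have taken lorcaserin. Relatedness is therefore something the pilot should help establish, and it makes a poor condition for writing an event down.

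Relatedness is also the judgement most easily influenced by knowing the treatment. The arms differ only in the first two weeks, so that period is the only controlled safety comparison. If the code may be broken to decide relatedness, the classification of an event in that window need not be blinded. Because unblinding also removes the participant from the final analyses, the participants most likely to drop out of the safety table are those whose events were worrying enough to prompt a code break.

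**Working it through.** The plan gives no adverse-event rate, relatedness rate or unblinding rate, so there is no planned figure to reproduce. The check sets the rules side by side.

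**1. Which events does each sentence reach?** Severity is intensity and seriousness is outcome; the protocol defines neither. Read literally:

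| Event | DSMP recording sentence | SAE sentence in Risk/Benefit (SAE = severe) | SAE Reporting Plan |
|---|---|---|---|
| Severe, judged unrelated | Yes, if a severe event counts as a severe side effect | Yes | No |
| Serious, not severe, possibly related | Yes | No | Yes |
| Serious, not severe, judged unrelated (e.g. a short hospital admission) | No | No | No |
| Neither severe nor serious, judged unrelated | No | No | No |

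The third row is the gap. It closes only if SAE in the Risk/Benefit Assessment is read as serious adverse event, against its own expansion there.

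**2. What is captured without a filter?** Side effects are rated by questionnaire at P1, P2, P3 and C1-C4, which is 3 + 4 = 7 sessions, in both arms, with staff blinded by default except for two roles. This feeds the planned tabulation directly. The questionnaires' content is not described, so it cannot be determined whether they would pick up an unlisted medical event or an admission. Spontaneous reports go to medical staff; the text does not say they are logged.

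**3. Can the code influence the record?** The code may be opened to decide relatedness, and no rule requires the judgement to be entered first. Relatedness is one of the two criteria in the recording sentence. The text therefore permits an unblinded classification; it does not say that an event already reported would then be discarded.

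**4. Can an event leave the analysis?** Yes, by a stated rule. A code break removes the participant's data from the final analyses, with no exception for safety data. The participant leaves both numerator and denominator.

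**5. What is one event worth?** The missed event is an assumption.

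- One event in an arm: 1/30 = 3.3 percentage points. Pooled: 1/60 = 1.7 points.
- Exact one-sided 95% upper bound with 1/60: the 95th percentile of Beta(2, 59) = 7.66%.
- If that event is not recorded, 0/60: 1 − 0.05^(1/60) = 4.87%.
- If that participant is excluded, 0/59: 1 − 0.05^(1/59) = 4.95%.

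These bounds illustrate scale only. The plan's 90% intervals are for abstinence and weight, and none is planned for side effects.

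**6. Is power the issue?** No. With effect size 0.8, 30 per group and one-sided alpha 0.05, the noncentrality is 0.8/√(1/30 + 1/30) = 3.10 on 58 degrees of freedom, giving 92.2% power and agreeing with the plan's figure of over 90%. Excluding five participants from one arm gives 0.8/√(1/25 + 1/30) = 2.95 on 53 degrees of freedom and 89.8%. The loss that matters is of safety data.

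**The case against.** A reader might infer three stronger things, and the documents support none of them.

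- **That adverse events are recorded only if severe or related.** The DSMP sentence contains no such restriction and can be read as describing the route to the IRB. Side effects are collected unfiltered at seven sessions, and participants are told to report any of them. This part of the objection stands for side effects. It does not settle what happens to other medical events, for which the DSMP sentence is the only recording rule.
- **That serious events judged unrelated go unrecorded.** This is stated nowhere. The Risk/Benefit Assessment sends SAEs to the IRB without a relatedness condition, and the Reporting Plan's condition governs expedited reporting, where a relatedness criterion is reasonable. What remains is a narrow class, serious but not severe and judged unrelated, which may be missed because the abbreviation is expanded as severe.
- **That capture differs by arm and biases the tolerability comparison.** The questionnaires are the same in both arms. The recording criterion is association with the study, and Group B also wears a 21 mg nicotine patch with its own listed side effects, so learning that the tablet was placebo does not make an event unrelated. An event that leads to unblinding has already reached medical staff. Bias through the recording filter is not shown.

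It is also fair to say that definitions may sit in the Center's standard operating procedures or the institutional policies to which the protocol refers. Those are not available here. They would not remove the inconsistency within the protocol or the exclusion of unblinded participants.

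**Conclusion.** The point holds in a limited form. For events outside the side-effect questionnaires, the stated recording rule depends on severity or possible association with the study. Relatedness may be judged with the code known. The two serious-event statements conflict on relatedness and terminology, so a serious, non-severe, unrelated event may not be captured. The questionnaire-based tabulation is not touched by that filter. It is exposed by a different route, since a code break made to decide relatedness takes the participant out of the final analyses.

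The size is unknown and probably small. One event is 3.3 points in an arm of 30, and a pooled upper bound would read about 4.9% instead of 7.7% if a single event in 60 were lost. This assumes that SAE is read as the protocol expands it, that the questionnaires do not reliably capture other medical events, and that the exclusion after unblinding applies to safety data as written.

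**What to change.** 1. **Data Safety Monitoring Plan:** state that all adverse events are recorded from first dose to last contact, whatever their severity or judged relation to treatment. Make relatedness a field in the record, completed and dated before any code break.
2. **Emergency Unblinding:** do not use the code break to assign relatedness. Leave unblinding for participant safety to the study physician, as now. State that the safety data of unblinded participants stay in the side-effect tabulation, with the unblinding flagged.
3. **Risk/Benefit Assessment, Serious Adverse Event Reporting Plan and DSMP:** reconcile the wording. Define adverse event and serious adverse event, use the latter term throughout, record all serious events, and use relatedness only as the criterion for expedited reporting.

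The cost is wording changes and a few more log entries, some for incidental events, in about 60 participants. No visits, tests or staff are added.

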STUDY TITLE: Combination Nicotine Patch / Lorcaserin for Smoking Cessation

NCT ID: NCT02906644

DOCUMENT VERSION DATE: February 12, 2018

Combination Nicotine Patch / Lorcaserin for Smoking Cessation

PI: [name].

Co-PI: [name].

PURPOSE OF THE STUDY:

This study proposes to investigate the potential efficacy of a combination of two FDA-approved agents, nicotine patch and lorcaserin, for smoking cessation treatment. The nicotine patch which provides a sustained low dose of nicotine is a nicotine receptor agonist. Lorcaserin, a serotonin 5-HT2C agonist, is a drug that is FDA-approved for weight loss, and has also recently been shown to be efficacious in a Phase II trial for smoking cessation (Shanahan et al, 2015). Given that these drugs act through distinct mechanisms it is hoped that the combination will prove more efficacious than either drug alone.

The aims of this small-scale (N=60) clinical trial are as follows:

- 1) To compare the efficacy of the nicotine patch / lorcaserin combination treatment vs. the nicotine patch alone in terms of leading to a reduction in ad libitum smoking behavior, withdrawal symptoms and time-to-lapse in a simulated quit-smoking situation;
- 2) To assess the tolerability of the combination treatment in terms of side effect frequencies and adherence to taking the medications;
- 3) To obtain an estimate of the smoking abstinence rate 10 weeks after a target quit-smoking date in smokers receiving combination treatment. Because the dichotomous outcome of abstinence vs. smoking is relatively insensitive from a statistical standpoint, no attempt will be made in this study to directly compare abstinence rates with the nicotine patch / lorcaserin combination vs. the nicotine patch alone. Instead, all participants will ultimately receive the combination treatment when making a quit-smoking attempt, yielding a larger sample with which to estimate the abstinence rate using combination treatment. This estimate will be compared with historical data on abstinence rates in a similar population of smokers;

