- 4) To assess weight gain after quitting smoking. Lorcaserin has been shown in the above-cited Phase II study to prevent weight gain, with subjects at Week 12 losing a small amount of weight relative to baseline (-0.41 kg), as compared to gaining +0.73 kg on placebo treatment. We predict that there will be, on average, no weight gain in this study, in contrast to historical data from recent clinical trials in our Center consistently finding a weight gain of approximately 2 kg in abstinent smokers at week 12 after quitting smoking.

The results pertaining to tolerability and efficacy obtained in this study will serve as useful pilot data for a future grant application that would propose to conduct a well-powered clinical trial comparing combination treatment to each agent alone and to placebo.

BACKGROUND & SIGNIFICANCE:

Cigarette smoking remains the leading cause of preventable disease and death in developed countries, due principally to its contributions to heart disease, chronic obstructive pulmonary disease (COPD), and cancer (Lando & Wilson, 2010). The annual death toll in the U.S. from diseases caused by smoking has been increasing steadily and is estimated to be the highest ever, 540,000/year (Carter et al., 2015). Importantly, smoking cessation leads to a substantial reversal of the risks borne by smokers (Kenfield et al., 2008). However, no new medications have been approved for smoking cessation treatment since FDA approval of varenicline in 2006. In fact, the rate of decrease in the prevalence of smoking has slowed in recent years, with over 45 million Americans continuing to smoke (CDC, 2014). Thus there is an urgent need for more effective therapeutic approaches that can be tailored to specific subpopulations of smokers and for guidance to medical providers.

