DATA ANALYSIS & STATISTICAL CONSIDERATIONS

The primary outcome measure will be the time-to-lapse during the laboratory session. McKee et al. (2012) reported an effect size of ~0.8 on this measure, and obtained significant results assessing the therapeutic effects of bupropion and varenicline with n=20 per group. With n=30 per group in the proposed study, and using a one-tailed alpha=0.05 (the hypothesis is one-tailed inasmuch as there would be no interest in pursuing the development of lorcaserin unless an increase in time-to-lapse is demonstrated), we should obtain over 90% power to detect a comparable effect. Secondary outcomes that will be compared between groups include the percent reduction in ad libitum smoking during the first 2 weeks, and withdrawal symptoms reported after 2 hours of smoking abstinence in the laboratory, measures that have been sensitive to treatment in our previous studies of nicotine replacement therapy (NRT) and other treatments. The two treatment groups will be compared on these measures using ANOVA-based statistical methods.

Continuous abstinence from smoking during weeks 7-10 after the quit date will also be tabulated, and 90% confidence intervals will be calculated. Abstinence will also be correlated with the reduction in ad libitum smoking in the first 2 weeks to determine whether smoking reduction may be a useful early marker of therapeutic efficacy. Among smoking-abstinent participants, weight gain relative to baseline will also be assessed, and 90% confidence intervals will be calculated.

Tolerability of treatment will be assessed by tabulating side effect frequencies and degree of adherence to taking medications (percent of total doses taken, assessed by self-report diaries and counts of returned medications at each session).

DATA & SAFETY MONITORING

Description of BP monitoring procedures after study enrollment

After study enrollment, if blood pressure during return sessions is above 160/100, then the following actions will be taken to enhance subject safety:

- If BP >210/100 with symptoms of malignant hypertension: stop experiment interventions and refer to appropriate medical treatment. Resume participation and continue to be monitored if BP is no greater than 140/100.

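### Emergency-unblinded participants are dropped from every final analysis, so safety-driven removals after randomisation distort the side-effect tables and discard recorded outcomes

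*Combined protocol and SAP*

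**What the plan says.** The rule is in the Emergency Unblinding section, under Data & Safety Monitoring: "If unblinding occurs, that subject's data will be censored and will not be included in final data analyses".

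The same section sets the trigger. "Emergency unblinding will occur under the discretion of the study physician" or a physician assistant, "in any situation in which unblinding is deemed necessary to ensure or promote the safety of a study participant". The examples include managing a side effect, advising on future drug reactions, uncovering safety information about the drug, and deciding whether an adverse event is related to the study.

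Aim 2 in the Purpose section is: "To assess the tolerability of the combination treatment in terms of side effect frequencies and adherence to taking the medications". The Data Analysis & Statistical Considerations section carries it out: "Tolerability of treatment will be assessed by tabulating side effect frequencies and degree of adherence to taking medications". That section defines neither an intention-to-treat set nor a safety set. The Purpose section also says what the results are for: "The results pertaining to tolerability and efficacy obtained in this study will serve as useful pilot data for a future grant application".

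Safety reporting runs separately. Under the Data Safety Monitoring Plan, "severe side effects and adverse events potentially associated with the study will be examined, recorded and then reported to the IRB".

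**The concern.** The rule removes people after randomisation for a reason tied to an outcome that the trial is meant to measure. Unblinding is discretionary and need not follow severity. Still, a participant whose code is broken for safety is likely to have had a notable side effect, and that is the participant who then leaves the side-effect tables.

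Three analyses are exposed:

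- **Tolerability (Aim 2).** Removing an affected participant always lowers the tabulated frequency, because (x−1)/(n−1) is below x/n whenever x < n. These frequencies are intended as pilot data for a larger trial, where an understated rate would carry over into planning.
- **Time-to-lapse (primary).** This is measured once, at the P2 laboratory session. An unblinding after P2 cannot affect a value already recorded, yet the wording deletes it. Deletions related to side effects can also unbalance the randomised comparison, in a direction that cannot be known beforehand.
- **Abstinence (Aim 3).** The participant leaves the denominator.

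**Working it through.** **Inputs from the documents.** 30 per group, effect size about 0.8, one-tailed alpha 0.05, stated power over 90% (Data Analysis & Statistical Considerations); 60 randomised in total. **Assumed, because the documents give no figure:** the number unblinded, k; the number with a given side effect, x; and how far the removed participants lie from the rest of their arm on time-to-lapse.

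**1. The plan's own figure.** Two-sample t test, noncentrality 0.8 × √(30×30/60) = 3.10, 58 degrees of freedom, one-tailed 0.05: power 92.2%. The normal approximation gives 92.7%. The stated figure of over 90% reproduces.

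**2. Side-effect frequency.** If k of the x affected participants are removed, the tabulated rate is (x−k)/(n−k).

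| True count | k = 1 | k = 2 | k = 3 |
|---|---|---|---|
| 3/30 = 10.0% | 2/29 = 6.9% | 1/28 = 3.6% | 0/27 = 0% |
| 6/30 = 20.0% | 5/29 = 17.2% | 4/28 = 14.3% | 3/27 = 11.1% |
| 3/60 = 5.0% | 2/59 = 3.4% | 1/58 = 1.7% | 0/57 = 0% |

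Exact (Clopper-Pearson) two-sided 95% upper limits: 26.5% for 3/30, 22.8% for 2/29 and 12.8% for 0/27.

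**3. Error rate of the primary test.** Suppose there is no treatment effect, and k participants lying δ SD from the rest of the lorcaserin arm are deleted. The mean of those remaining then differs from the full-arm mean by −δk/30. For k = 1 and δ = −1 this is +0.033 SD, and the noncentrality is 0.033 × √(29×30/59) = 0.128. One-tailed rejection rates at a nominal 5%, comparing (30−k) with 30:

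| δ (SD) | k = 1 | k = 2 | k = 3 | k = 4 |
|---|---|---|---|---|
| −0.5 | 5.7% | 6.4% | 7.2% | 8.1% |
| −1.0 | 6.4% | 8.2% | 10.2% | 12.4% |
| +0.5 | 4.4% | 3.8% | 3.4% | 2.9% |
| +1.0 | 3.8% | 2.9% | 2.2% | 1.6% |

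A simulation of 200,000 runs agrees: for k = 3 it gives 10.1% at δ = −1 and 2.2% at δ = +1.

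**4. Power.** With no shift and all deletions in the lorcaserin arm, power at 0.8 is 91.8% for one removed, 91.4% for two, 90.9% for three and 90.4% for four. Bias matters here more than power.

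**5. Abstinence.** If 13 of 60 were abstinent (assumed; 21.7%) and three smokers were removed, the rate would be 13/57 = 22.8%. This is a small change. No effect on the weight result is claimed.

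**The case against.** The strongest objection is that the rule may hardly ever operate. The arms differ only in the first two weeks. After P2 everyone is known to receive patch plus lorcaserin, so there is little reason to break the code, and most side-effect assessments (P3 and C1 to C4) fall in that later period. The larger figures need implausible combinations: 0/27 requires every affected participant to be unblinded, and 12.4% requires four of 30 in one arm, each with a P2 value and averaging 1 SD below the rest. Someone unblinded early may never reach P2, and then the rule deletes no primary value. With one removal, the 95% intervals for 3/30 (2.1% to 26.5%) and 2/29 (0.8% to 22.8%) overlap almost entirely. Before P2 only Group A receives the combination, so removing a Group B participant takes out no combination side effect from that period. Events still reach the IRB. Finally, the word censored could mean truncation at unblinding, and the rule does not name the side-effect tables.

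Most of this stands as a limit on size. The one- and two-deletion columns are the realistic ones, and safety oversight is intact. It does not rescue the rule. The second half of the sentence, which keeps the data out of the final analyses, does not fit a reading of truncation only, and its wording is unqualified. It has no time limit, so a P2 value already recorded is lost if unblinding comes later. IRB reporting does not put a participant back into the Aim 2 tables.

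**Conclusion.** The concern holds. As written, the rule excludes participants after randomisation for safety reasons, from all final analyses and without a time limit, and no defined analysis set restores them.

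For tolerability the direction is known: each unblinding prompted by a side effect lowers that side effect's tabulated frequency, for example from 10.0% to 6.9% with one removal from 3/30. For the primary comparison the direction is unknown: one deletion lying 0.5 to 1.0 SD from the rest of the lorcaserin arm moves the 5% error to between 5.7% and 6.4%, or to between 4.4% and 3.8%. The effects on power and abstinence are small. All sizes rest on assumed counts and shifts, and with no unblindings there is no effect. The text should be corrected before analysis; the practical consequence is likely to be limited.

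**What to change.** Replace the exclusion sentence in Emergency Unblinding with wording to this effect:

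> All randomised participants stay in the analysis by assigned group. Unblinded participants stay in every side-effect and adherence table and in the abstinence denominator. Outcomes recorded before unblinding are always used. Outcomes recorded after unblinding are kept and flagged, and their exclusion is shown only as a sensitivity analysis.

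Report the number, arm and timing of unblindings. The decision to unblind is unchanged.

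The cost is a short text change, with no added data or participants. The downside is that a few self-reports made after unblinding are retained, which the sensitivity analysis covers. A P2 value that was never recorded stays missing; this change does not address that, nor does it say how an unknown abstinence status is to be counted.
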